A Trauma-Informed Intervention for Positive Youth Development and
Teacher Wellness in Rural Montana

[name]

September 1, 2021

Clinical Trial # NCT05085392

Statistical Design and Power

Study design

This study is a non-randomized, Phase I clinical trial. Participants will be high school students and teachers in southwest Montana. In the first year, 30 teachers from the same school district will be recruited to participate in a virtually-delivered trauma-informed yoga intervention (heart rate variability data will be gathered from a group of high school students to assess utility for the measure in year 2). In the second year, we will expand the intervention to high school students in Livingston city and rural Park County schools, recruiting 30 students in each area to participate in a synchronous, virtually-delivered, trauma-informed yoga intervention during their health enhancement classes. In addition, 30 teachers from the rural Park County schools will be recruited to participate in the same virtually-delivered, trauma-informed yoga intervention offered to Livingston teachers concurrently.

In each year, participant assessments (surveys, salivary cortisol, and heart rate variability(HRV)) will be administered prior to intervention and immediately after the intervention at 6 weeks. Follow-up assessments will be conducted in the fall semester following each intervention to measure persistence of the treatment. Thus, Livingston teachers may have up to six time points of data collection, while Park County students and teachers and Livingston students will have up to three. In addition, salivary cortisol and HRV will be collected at the midpoint of the intervention (3 weeks) each year. Measures collected are detailed in Table 1.

Table 1. Measures recorded for students and teachers, with collection timeline and validity measures.

Description of Measure	Source (if applicable)	Timeline for Collection	Cronbach's Alpha/Validity & Reliability
Center for Youth Wellness ACE-Q Self-Reporting Screener for Teens (Adolescents Only)	Burke-Harris & Renschler, 2015	Pre-intervention (in order to determine ACE scores of participants)	Longitudinal testing currently underway to measure content and construct validity/reliability
Generalized Anxiety Disorder Scale (GAD-7) (Adolescents and Teachers)	Spitzer et al., 2006	Pre- and post-intervention	Cronbach's alpha: .79-.91 Reliability = .85 Validity = 73.3%
Patient Health Questionnaire for Depressive Symptomology (PHQ-A for adolescents, PHQ-9 for Teachers)	Johnson, 2002	Pre- and post-intervention	Chronbach's alpha = .835 Reliability = .875 Validity = 89.5%
Connor-Davidson Resilience Scale (CD-RISC) (Adolescents and Teachers)	Connor & Davidson, 2003	Pre- and post-intervention	Chronbach's alpha = .94 Reliability = .96
Columbia Suicidality Screener (C-SSRS) (Adolescents Only)	Greist et al., 2014	Pre- and post-intervention	Cronbach's alpha: .81-.95 Reliability = .97 Validity = 99%
Professional Quality of Life Index (Pro-QOL)	Hudnall Stamm, 2009	Pre- and post-intervention	Cronbach's alpha: .90 Reliability = .80-.90

(Teachers Only)			
Teachers' Sense of Self-Efficacy (Short Form) (Teachers Only)	Tschannen-Moran & Woolfolk-Hoy, 2001	Pre- and post-intervention	Cronbach's alpha: .90 Reliability = .74
Cortisol salivary assays (Adolescents and Teachers)	Salimetrics Laboratories	Pre (beginning of week 1)-, mid- (week 3) and post-intervention (end of week 6)	Mean accuracy of salivary cortisol testing > 90%
Heart rate variability data (Adolescents and Teachers)	HeartMath Institute	Pre- (1 week prior to intervention to establish a baseline), mid- (week 3) and post-intervention (at conclusion of week 6)	Pearson correlation between electrocardiogram (ECG) and ear clip pulse plethysmograph (PPG) device (Em Wave Pro Plus) mean resting baseline = .997*, p <0.01; RMSSD Pearson correlation = .958*, p < 0.01
Collection of secondary data, including attendance and academic data (MAPS benchmark/progress monitoring standardized assessment scores, attendance, and office referrals) (Adolescents Only)	N/A	Office referrals/behavioral data: Collected 8 weeks prior to study and during 8 weeks of intervention for comparison Attendance data: Collected 8 weeks prior to study and during 8 weeks of intervention for comparison MAPS: Pre- and post-intervention	MAPS Data: Pearson correlation coefficients range from .76-.82 in reading and .82-.86 in mathematics Other measures: N/A

Power considerations

This is an early-phase trial, the results of which will be used to inform full power analyses for future clinical trials. We do not expect to be powered to detect small intervention effects.

However, as a preliminary assessment of power, we consider the power of a paired t-test comparing pre- and post- intervention scores on the various response measures, including survey scales, cortisol, and HRV. We compute power in terms of Cohen's d, a standardized effect size measure that describes the impact of the intervention in terms of the number of standard deviations that the effect is equivalent to (so an effect of 5 points on a scale with SD 20 would have a Cohen's d of 0.25). On this scale, an effect size of 0.2 is typically considered "small", 0.5 "moderate", and 0.75 "large". This may not align with clinically meaningful differences in outcome measures, however.

For comparisons within intervention groups in their first (and sometimes only) year of intervention, we expect to have 30 participants in each group (Livingston students, Livingston teachers, rural students, rural teachers). Assuming a Type I error rate of $\alpha = 0.05$, we achieve 80% power to detect a Cohen's d of 0.53, and 90% power to detect a Cohen's d of 0.61. Thus, the study is adequately powered to detect moderate-to-large effects of the intervention. The study design will allow us to estimate the magnitude of effects, intra-class correlations by school and classroom, and the variability of intervention impacts—all the inputs needed to perform a formal power analysis for a future Phase III trial. Full power curves for $n = 30$ and $n = 15$ participants are given in Figure 1.

[figure not shown]

Figure 1. Power curves for sample sizes of 15 and 30. Solid black line indicates 80% power and dashed line indicates 90% power.

Statistical Analysis Plan

For each outcome, we will compute the change in the scale score or biomarker value from baseline to post-intervention (post – pre) and compute unadjusted averages and standard deviations. These computations will be done within participant group (Livingston students, Livingston teachers, rural students, rural teachers).

We will also obtain adjusted estimates using mixed effects linear regression models of post-test score on pre-test score with demographic factors and random effects for school and intervention group nested within school (Laird & Ware 1982). This will allow us to estimate intra-class correlations for intervention group and school, which will be required for sample size estimation in a full efficacy trial.

We propose the following model for the individual response (anxiety, depressive symptoms, etc.), denoted Y_{ijk} , where $i = 1, \dots, I$ indexes school, $j = 1, \dots, J$ indexes intervention group (only needed if there are multiple health education classes receiving the intervention in a school), and $k = 1, \dots, N$ indexes participants within groups.

$$\begin{aligned}
 Y_{ijk} &= Z_{ijk} \theta + X_{ijk} \delta + \alpha_i + \beta_{j(i)} + \varepsilon_{ijk} \\
 \alpha_i &\sim N(0, \tau^2) \\
 \beta_{j(i)} &\sim N(0, \omega^2) \\
 \varepsilon_{ijk} &\sim N(0, \sigma^2)
 \end{aligned}$$

Thus, α_i represents a random effect for school i , with variance τ^2 , $\beta_{j(i)}$ represents a random effect corresponding to group j in school i , with variance ω^2 . We model this as a function of Z_{ijk} , the pre-intervention score for participant k in group j in school i , and X_{ijk} , the set of other modeled covariates, centered at their means. This means that the intercept parameter θ gives the expected effect of the program for a student or teacher with “average” demographics and other covariate values after controlling for within-school and within-group correlation. We can use the estimates of the random-effects variances and the residual variance to produce estimates of the intra-class correlations for school and for intervention group.

This is a Linear Mixed Effects (LME) model. As all primary and secondary response variables are continuous and may reasonably be expected to be normally distributed we can implement the model using restricted maximum likelihood (Laird & Ware 1982) using the `lme4` package in **R** (Bates et. al., 2015).

Biomarker analyses. Salivary cortisol and HRV will also be collected mid-intervention.

To fully characterize temporal patterns in these outcomes, we will use a different LME model that captures the full trajectory over time. In this case, we propose the following model for the individual response, denoted Y_{ijkt} , where $i = 1, \dots, I$ indexes school, $j = 1, \dots, J$ indexes intervention group (only needed if there are multiple health education classes receiving the intervention in a school), $k = 1, \dots, N$ indexes participants within groups, and $t = 1, \dots, 3$ indexes the time point of the observation.

$$Y_{ijkt} = \theta T_{ijkt} + X_{ijk} \delta + \alpha_i + \beta_{j(i)} + \gamma_{k(ij)} + \varepsilon_{ijkt}$$

$$\alpha_i \sim N(0, \tau^2)$$

$$\beta_{j(i)} \sim N(0, \omega^2)$$

$$\gamma_{k(ij)} \sim N(0, \vartheta^2)$$

$$\varepsilon_{ijk} \sim N(0, \sigma^2)$$

Thus, α_i represents a random effect for school i , with variance τ^2 , $\beta_{j(i)}$ represents a random effect corresponding to group j in school i , with variance ω^2 , and $\gamma_{k(ij)}$ represents a random effect corresponding to student k in group j and school i , with variance ϑ^2 . We model this as a function of T_{ijkt} , the time of the t^{th} cortisol or HRV measure for participant k in group j in school i , and X_{ijk} , the set of other baseline covariates included in the model, centered at their means. We can also consider a random slope model with varying slopes for each student over time if model diagnostics suggest this more complex model will be a better fit to the data.

References:

1. Nan M. Laird and James H. Ware (1982) Random-effects models for longitudinal data. *Biometrics* 38:963-974
2. Douglas Bates, Martin Maechler, Ben Bolker, and Steve Walker (2015). Fitting Linear Mixed-Effects Models Using lme4. *Journal of Statistical Software*, 67(1), 1-48

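### The fall follow-up meant to measure persistence has no stated analysis, and the biomarker trajectory model, as most naturally read, fits only a straight line

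*Combined protocol and SAP*

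**What the plan says.** **Schedule.** Under Study design, "participant assessments (surveys, salivary cortisol, and heart rate variability(HRV)) will be administered prior to intervention and immediately after the intervention at 6 weeks". The next sentence adds the later visit: "Follow-up assessments will be conducted in the fall semester following each intervention to measure persistence of the treatment". The section then counts occasions: "Livingston teachers may have up to six time points of data collection", and up to three for the other groups. The midpoint is separate: "In addition, salivary cortisol and HRV will be collected at the midpoint of the intervention (3 weeks) each year". The section closes with "Measures collected are detailed in Table 1".

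**Table 1.** The survey scales are listed as pre and post only. Cortisol and HRV are listed as pre, mid (week 3) and post (end of week 6). The cortisol baseline is at the start of week 1 and the HRV baseline one week before the intervention. No row mentions a fall collection.

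**Analyses.** The Statistical Analysis Plan has three:

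- an unadjusted summary, to "compute the change in the scale score or biomarker value from baseline to post-intervention";
- an adjusted analysis by "mixed effects linear regression models of post-test score on pre-test score with demographic factors" and random effects for school and group;
- under Biomarker analyses, a longitudinal mixed model with t = 1 to 3, introduced because of the mid-intervention samples and meant to describe the full course over time. Its mean is θT plus centred covariates, where T is the time of the measurement. The only extension offered is a random slope per student.

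**The concern.** The plan schedules a visit for a stated purpose, persistence, and then gives no contrast, model term or estimate for it. Whoever analyses those data would have to choose the measures and the comparison after seeing them. The silence of Table 1 leaves it unclear which measures the visit includes.

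The second part concerns fit to purpose. A model meant to describe the pattern over three visits should be able to show a bend at the middle one. If T enters as a continuous time with a single coefficient, it cannot, and the midpoint collection does not serve the purpose for which the model was introduced.

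**Working it through.** **1. The plan's own figure.** Two-sided paired t-test, n = 30, α = 0.05, df = 29, noncentrality d√n. At d = 0.53 the noncentrality is 0.53 × 5.477 = 2.90 and power is 80.1%. At d = 0.61 it is 3.34 and power is 89.8%. Both match the plan. They concern pre versus post only, and nothing below changes them.

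**2. Counting occasions.** Pre + post + fall = 3 per cycle, which is the plan's up to three. Over two years this is 2 × 3 = 6, which is the Livingston teachers' up to six. So the count includes the fall visit and leaves out the midpoint.

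| | Study design | Table 1 | Used in a stated analysis |
|---|---|---|---|
| Surveys | pre, post, fall | pre, post | pre, post |
| Cortisol, HRV | pre, mid, post, fall | pre, mid, post | pre, mid, post |

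The post visit is fixed at 6 weeks, so post cannot be read as fall. If Study design governs, biomarkers have four occasions per cycle and the model holds three. If Table 1 governs, the model omits nothing that is collected.

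**3. Weight of the midpoint on a straight line.** With an intercept (assumed, because the printed equation shows none) and complete data, the slope weight at each time is (T − mean T)/SS.

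- Times 0, 3, 6: mean 3, SS = 9 + 0 + 9 = 18, weights −0.167, 0, +0.167. The midpoint share is 0%.
- Times −1, 3, 6 (HRV): mean 2.667, SS = 13.44 + 0.11 + 11.11 = 24.67, weights −0.149, 0.0135, 0.135. The midpoint share is 0.0135/(0.149 + 0.0135 + 0.135) = 4.5%.

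Take an assumed effect of 0.53 SD of the change:

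- Early plateau (0, 0.53, 0.53) at 0/3/6: slope 0.53 × 0.167 = 0.088 per week.
- Late effect (0, 0, 0.53) at 0/3/6: the same slope, 0.088.
- HRV times: plateau 0.53 × (0.0135 + 0.1351) = 0.079; late 0.53 × 0.1351 = 0.072.
- Mid-only (0, 0.53, 0) at 0/3/6: slope 0.

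At 0/3/6 the fitted pre-to-post change is 6 × slope = post − pre exactly, so that contrast is unbiased and has the same variance as under a visit factor.

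**4. What this does to power.** Simulation (20,000 to 40,000 runs) with n = 30, random intercept, complete data and effects in SD of the change. All patterns are assumed.

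| Pattern (pre, mid, post) | Slope | Mid minus pre |
|---|---|---|
| Linear (0, 0.265, 0.53) | 82% | 30% |
| Late (0, 0, 0.53) | 80% | 5% |
| Early plateau (0, 0.53, 0.53) | 80% | 81% |
| Half lost by post (0, 0.53, 0.265) | 26% | 82% |
| Mid-only (0, 0.53, 0) | 3% | 82% |

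**5. Precision of a fall contrast.** The 95% CI half-width in SD of that change is t(0.975, n − 1)/√n. It is 0.37 at n = 30, 0.46 if 21 return and 0.55 if 15 return (return rates assumed). Multiplying the n = 30 value by √(1 + (m − 1)ICC), with assumed cluster size m:

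- m = 10, ICC 0.01: 0.373 × 1.044 = 0.39.
- m = 15, ICC 0.10: 0.373 × 1.549 = 0.58.

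These keep 29 df, which is optimistic with few clusters.

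**The case against.** Table 1 is where the plan says its measures are detailed, and its three biomarker times agree with t = 1 to 3. A reader might infer that the biomarker model certainly drops a collected visit. The documents do not support that, because they conflict on whether cortisol and HRV are taken in the fall. This part of the point is conditional.

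The notation is also loose. θ is called an intercept in the first model although it multiplies the pre-score there, and the biomarker equation prints no intercept. T could be meant as visit indicators, in which case the mean is unrestricted. Without an intercept the weights at 0/3/6 would be 0, 3/45 = 0.067 and 6/45 = 0.133, so the midpoint would count. Both objections are fair. Still, time of measurement with varying slopes is continuous-time language, and a mean forced through zero is not a sensible reading for cortisol or HRV.

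A reader might also infer that the linear model is generally less powerful, or that the midpoint samples are of no use. Neither holds. The slope does better than mid minus pre for linear or late effects. The midpoint informs the slope when post samples are missing, and it informs the variance components, which the trial wants for later planning. Nothing in the documents suggests that the mid-only pattern is likely.

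Finally, this is an early-phase trial aimed at estimation. That limits the seriousness, but it also means that the estimates are the product, and persistence is one that the plan says it will measure.

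**Conclusion.** The point holds in two parts of different strength.

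The first is firm and textual. Persistence is a stated purpose, its visit is one of up to three occasions per participant (two of up to six for Livingston teachers), and no stated analysis uses it. Table 1 and Study design disagree on what is collected.

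The second is conditional on T being continuous and an intercept being present. The biomarker mean is then a straight line, random slopes do not bend it, and with complete data the midpoint has 0% of the slope weight at 0/3/6 and 4.5% for HRV. The cost runs from negligible (plateau, 80% versus 81%) to near total (mid-only, 3% versus 82%) under the assumed effect of 0.53. What is lost is the shape over time. The pre-to-post estimate is not biased at equal spacing with complete data, and the plan's power statement is correct.

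This should be put right before analysis. It does not undermine the pre-to-post results.

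**What to change.** 1. Reconcile Study design and Table 1: state for each measure whether it is collected in the fall.
2. For each measure collected then, report with 95% CIs fall minus pre (or the fall score in the same baseline-adjusted mixed model) and fall minus post. The first gives the change at fall, and the second shows how much of the post-intervention change is kept. State that, without a control group, both include time-related change.
3. In the biomarker model, code visit as categorical with an explicit intercept, and report mid minus pre and post minus pre with 95% CIs.
4. If biomarkers are collected in the fall, extend t to 4. Take the standard errors of the fall contrasts from paired differences, or from a covariance structure that does not force equal correlation between near and distant visits.
5. Do not add the fall visit to a linear time term. With fall at an assumed week 26, the slope weights are −0.0211, −0.0139, −0.0066 and 0.0416. A gain of 0.53 that is fully kept (0, 0.265, 0.53, 0.53) would be fitted as a pre-to-post change of 6 × 0.0149 = 0.09 (0.13 at week 20, 0.07 at week 32). The plan does not propose this model; the figures only warn against the obvious shortcut.

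**Cost.** SAP wording, a Table 1 correction and code, with no data beyond what Study design schedules. Categorical visit adds one fixed-effect term with three visits, or two with four. An omnibus visit test has less power than the slope if change is truly linear (72% versus 82% at an assumed d = 0.53, n = 30), so rely on the contrasts. At equal spacing with complete data, post minus pre keeps the same variance as the linear fit.

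### By default the adolescent suicidality screener (C-SSRS) is reported only as a net average change, so the number of students who newly screen positive or worsen is not reported

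*Combined protocol and SAP*

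**What the plan says.** All references are to the combined protocol and SAP.

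- **Table 1** includes the "Columbia Suicidality Screener (C-SSRS) (Adolescents Only"), collected pre- and post-intervention, the same entry as the GAD-7, PHQ and CD-RISC. Under Study design, assessments "will be administered prior to intervention and immediately after the intervention at 6 weeks".
- **Statistical Analysis Plan, descriptive part:** "For each outcome, we will compute the change in the scale score or biomarker value from baseline to post-intervention (post – pre"), and then "compute unadjusted averages and standard deviations", separately in the four participant groups, two of which are student groups. No measure is excepted.
- **Statistical Analysis Plan, adjusted part:** "mixed effects linear regression models of post-test score on pre-test score with demographic factors", with random effects for school and for intervention group within school. The plan states that "all primary and secondary response variables are continuous and may reasonably be expected to be normally distributed".
- The only outcomes given a different analysis are cortisol and HRV, under Biomarker analyses.

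The C-SSRS is not mentioned after Table 1. The document gives no scoring rule for it, no definition of a positive or worsened screen, no shift table, no count of students who change category and no safety analysis.

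**The concern.** A mean change is a net quantity. For a symptom scale that is often what one wants. For a suicidality screen in minors, a student who improves does not make up for a student who newly screens positive. What a reader will want to know is how many students worsened. A regression of post on pre does not report that either: it gives an average post score, adjusted for baseline and covariates. Replacing the normal model with a better one would not change this, because any correctly modelled average still nets the two directions.

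This is the only dedicated suicidality measure in Table 1, in a trial described as Phase I, where describing emergent harm is a natural task. If the plan is followed as written, the C-SSRS result could be a mean change near zero, read as no change, with no statement of how many students got worse.

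**Working it through.** **The plan's own figure.** Power considerations gives n = 30 per group, α = 0.05, and 80% power at d = 0.53 and 90% at d = 0.61 for a paired t-test. With the noncentral t (df = 29, noncentrality d√30, two-sided), power is 80.1% at d = 0.53 and 89.8% at d = 0.61. The figures reproduce, and nothing here disputes them.

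**Inputs.** n = 30 per student group is from Power considerations. The document gives no C-SSRS rates or levels, so every count below is an assumption for illustration.

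**Step 1, graded levels.** Suppose 2 students rise four levels, 8 fall one level and 20 do not move.

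- Mean = (2×4 − 8×1)/30 = 0.
- Sum of squares = 2×16 + 8×1 = 40, so SD = √(40/29) = 1.174.

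Two other patterns give the same pair of numbers:

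| Pattern (n = 30) | Sum | Sum of squares | Mean | SD | Worsened |
|---|---|---|---|---|---|
| 2 up four, 8 down one | 8 − 8 = 0 | 32 + 8 = 40 | 0 | 1.174 | 2 |
| 5 up two, 5 down two | 10 − 10 = 0 | 20 + 20 = 40 | 0 | 1.174 | 5 |
| 8 up one, 2 down four | 8 − 8 = 0 | 8 + 32 = 40 | 0 | 1.174 | 8 |

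The reported mean and SD therefore do not determine the number who worsened.

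**Step 2, 0/1 coding.** Let b be newly positive and c resolved. With b = c = 3, mean = (3 − 3)/30 = 0 and SD = √(6/29) = 0.455. Here the counts can be recovered:

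- b − c = n × mean = 0
- b + c = (n − 1)SD² + n × mean² = 29 × 0.455² = 6.0

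Hence b = c = 3. The information is present, but a reader has to work it out.

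**Step 3, dependence on balance** (0/1 coding; p from a paired t-test, used only as a yardstick):

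| New | Resolved | Mean change | p |
|---|---|---|---|
| 3 | 3 | 0 | 1.00 |
| 4 | 2 | (4 − 2)/30 = +0.067 | 0.42 |
| 6 | 0 | 6/30 = +0.20 | 0.012 |

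The mean hides balanced or nearly balanced movement. It does not hide movement in one direction on the scale of 6 students.

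**Step 4, the alternative summary.** If 3 students are positive at baseline, 30 − 3 = 27 can become positive. Three who do are 3/27 = 11.1%. The Clopper-Pearson limits are the 2.5% quantile of Beta(3, 25) and the 97.5% quantile of Beta(4, 24): 2.4% to 29.2%. With 6 positive at baseline it is 3/24 = 12.5% (2.7% to 32.4%). A finding of 0/30 would still have an upper limit of 1 − 0.025^(1/30) = 11.6%.

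McNemar's test would not help. It also tests net change, and 3 against 3 gives p = 1.00.

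**The case against.** The strongest reply has five parts.

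- **The C-SSRS is never named in the analysis section.** This stands. Table 1 lists measures recorded, and includes the ACE-Q, which is collected only at baseline and cannot have a change score. The rule reaches the C-SSRS by default, not by name. If it was meant to be excluded, it has no stated analysis, and the same addition is needed.
- **Mean and SD together give the counts.** This stands for 0/1 coding, as step 2 shows. A reader might infer that the number newly positive is always lost; that goes too far. It fails for graded levels (step 1). The document does not say which coding applies. The word screener does not settle it, since the ACE-Q carries the same word and is used to obtain scores.
- **Cancelling needs balanced movement.** This stands. If few students are positive at baseline, few can resolve, and emergence raises the mean. Offsetting is possible; the document does not show that it will happen.
- **Individual screens may be handled elsewhere.** A reader might infer that nobody would act on a positive screen. The document covers design, power and analysis only and cannot support that. The point here is reporting alone.
- **There is no comparison arm.** This stands. A reader might infer that newly positive students would show harm from the program. Counts would describe emergence and could not attribute it.

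**Conclusion.** The point holds in a limited form. Followed as written, the plan's only C-SSRS results would be the mean and SD of change and a linear model of post on pre. None of these states how many students newly screened positive or worsened. With graded levels that number cannot be worked out from the mean and SD: in the assumed example, 2, 5 or 8 students worsening out of 30 all give mean 0 and SD 1.174. With 0/1 coding it can be back-calculated but is not reported.

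This rests on reading the rule for each outcome as covering the C-SSRS, and on assumed movement counts, since the document gives no rates. How often a mean near zero would hide worsening in this trial cannot be estimated from the document. The change is worth making because a better summary needs no new data.

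**What to change.** Add to the Statistical Analysis Plan:

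1. The C-SSRS levels used for analysis, and what counts as positive and as worsened.
2. For each student group, a pre-by-post shift table, with missing post-screens shown.
3. From that table, each with an exact 95% CI: newly positive among those negative at baseline, worsened among those who could worsen, and, separately, resolved among those positive at baseline.
4. A statement that this table is the main C-SSRS result, presented descriptively as a safety outcome. The mean change may stay as a supplement but should not be the basis for a statement of no change.

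Study design also mentions fall follow-up assessments, while Table 1 lists the C-SSRS only before and after the intervention. If it is repeated in the fall, the same table should be given for that time point.

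The cost is a short SAP paragraph and one table per student group, from data already planned. The intervals will be wide at about 30 students per group, and the single-arm design does not allow the counts to be attributed to the program.

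### Without a control arm, an intercept at sample-centred covariates does not give a sound interval for population mean change, because the default standard error treats the sample means as known

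*Combined protocol and SAP*

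**What the plan says.** Under Study design, the trial is described thus: "This study is a non-randomized, Phase I clinical trial". No control arm is described.

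Under Power considerations, the reference analysis is a paired t-test of pre against post within each participant group: "we expect to have 30 participants in each group", and "we achieve 80% power to detect a Cohen's d of 0.53".

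The Statistical Analysis Plan reports the unadjusted mean and SD of post minus pre by group, and then adds: "We will also obtain adjusted estimates using mixed effects linear regression models of post-test score on pre-test score with demographic factors". School and class-within-school enter as random effects. The text after the model equation describes X as "the set of other modeled covariates, centered at their means", and says that the intercept parameter θ "gives the expected effect of the program for a student or teacher with" average demographics and covariate values. Fitting is by REML in lme4.

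The plan leaves four things open:
- The printed equation has no intercept; θ multiplies the pre-score Z.
- It is unclear whether Z is centred as well as X.
- It is not stated whether average means the sample or the population average.
- No standard error, interval or test for the adjusted effect is given.

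**The concern.** In a two-arm comparison, the error in the sample mean of a baseline covariate drops out of the treatment contrast. Here the effect is a level, not a contrast, and nothing drops out. If the covariates are centred at their sample means, the model-based standard error of the intercept reflects only residual scatter around the fitted line. It leaves out the fact that another sample of 30 would have had a different mean pre-score.

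With complete data and no clustering, the intercept of change on centred pre-score equals the unadjusted mean change exactly. The same estimate would then be reported twice, the second time with a narrower interval. A colleague who reads the adjusted result as evidence about participants in general would credit it with precision that it does not have.

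**Working it through.** **The plan's own figures.** Inputs: n = 30, alpha 0.05 and the paired t-test (Power considerations). With a noncentral t on 29 df, noncentrality d·sqrt(30) and a two-sided test, the detectable d is 0.529 at 80% power and 0.612 at 90%. This reproduces 0.53 and 0.61. A one-sided test would give 0.465 and 0.547. The power section thus rests on a two-sided 5% test of the population mean change.

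**Assumptions that the documents do not supply.** Pre-post correlation rho (0.3 to 0.8), equal pre and post SDs (set to 1), the variance explained by demographics, and the number of schools and the ICC where clustering is added.

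**Algebra, no clustering, pre-score centred, effect expressed as change.**
- Variance of the mean change: 2(1−rho)/n.
- Variance that the model reports for the intercept: (1−rho²)/n.
- When the population mean change is zero, the expected change at the sample-mean pre-score is (rho−1) × (sample mean − population mean). Its variance is (1−rho)²/n, and this is the missing part: (1−rho²) + (1−rho)² = 2(1−rho).
- Ratio of reported to required SE: sqrt((1−rho²)/(2(1−rho))) = sqrt((1+rho)/2).

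Example, rho = 0.5, n = 30: reported SE sqrt(0.75/30) = 0.158; required SE sqrt(1.00/30) = 0.183; ratio 0.866.

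| rho | Reported SE | Required SE | SE too small by | Simulated coverage of population mean change | Type I error |
|---|---|---|---|---|---|
| 0.3 | 0.174 | 0.216 | 19% | 89.3% | about 11% |
| 0.5 | 0.158 | 0.183 | 13% | 91.0% | about 9% |
| 0.7 | 0.130 | 0.141 | 8% | 93.1% | about 7% |
| 0.8 | 0.110 | 0.115 | 5% | 93.8% | about 6% |

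The paired t-test gives about 5% on the same data. The ratio does not involve n, so a larger sample does not help: at n = 60 and rho 0.5 the error is still about 9%. Three further covariates that explain 10% of the residual variance lower coverage to 87.0%, 89.8%, 91.9% and 92.8%.

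**Other readings of the same text.**
- *Target is the effect at the observed sample averages.* Coverage is 94.6% to 95.2% in all the n = 30 cases. No defect.
- *Only the demographics are centred and play this role.* The SE ratio is sqrt(1−R²) = 0.97, 0.95 and 0.89 for assumed R² of 0.05, 0.10 and 0.20; approximate coverage is 94.4%, 93.7% and 92.0%.
- *Pre-score not centred.* The intercept is the expected post-score at a pre-score of zero. If the mean pre-score lies 1 to 2 SD above zero and rho is 0.5 to 0.7, its SE is 1.2 to 2.1 times that of the mean change: wider, not narrower.

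**Clustering.** With a school random intercept (assumed 3 or 6 schools of 10, rho 0.5 to 0.7) and ICC 0, population coverage is 92.1% to 93.7% and sample-average coverage 95.3% to 95.8%. At ICC 0.1 they are 86.7% to 90.8% and 89.4% to 92.2%. Most of that second shortfall comes from using a normal quantile with few schools, not from centring.

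**The case against.** A reader might infer that the adjusted intervals in this trial will simply be too narrow and will exclude zero too often. The documents do not support so flat a statement, for these reasons:

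- The specified response is post-score, not change, and no intercept is printed. The error rates above describe one natural repair of the model, not the model as written.
- Centring is explicit for X only. If Z is left uncentred, the interval is wider.
- Average may mean the observed sample, and then the conditional SE is correct.
- No adjusted interval or test is promised, and the purpose given for the model is to estimate intra-class correlations.
- The inputs listed for the next trial are effect magnitude, ICCs and variability of impacts, not an intercept SE. The point estimate matches the unadjusted mean change in the simple case, so harm to later planning is limited.
- The unadjusted mean and SD of change already yield a paired interval. The repeated-measures biomarker model, with its participant effect and time coefficient, is not exposed to this mechanism.

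All of this stands as a limit on scope. It does not remove the point. An uncentred Z cannot give the program effect that the text describes, so centring Z is the reading closest to the stated aim. The paired t-test used for power targets the population mean change, and the results are meant to inform later trials. With no interval method named, default lme4 output is what an analyst would probably report. Adding the missing intercept and expressing the effect as change, with nothing further, leads straight into the understated SE.

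**Conclusion.** The point holds in conditional form. The post-on-pre model with an intercept read at centred covariates is not a sound source of an interval for the population mean change in this single-arm design. If the pre-score is centred at its sample mean and the effect is expressed as change, the default SE is too small by about 5% to 19%, and type I error at n = 30 is about 6% to 11%, for assumed rho of 0.8 down to 0.3 with equal SDs and no clustering. The shortfall is smaller if only demographics are centred, and absent if the target is the effect at the observed sample averages. The size is modest and rests on a correlation that the documents do not give. The plan should be changed here because it leaves the target, the centring and the interval undefined, and a better analysis costs little.

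**What to change.** 1. State that the target is the population mean change, the same quantity as in the paired t-test used for power.
2. Take the estimate and interval from a change-score model with school and class random effects and no centred person-level covariates. Alternatively, model pre and post jointly with a participant effect and a time term; let the time term vary by school and class if clustering of change is to be carried.
3. Keep the post-on-pre model for conditional ICCs only.
4. If a covariate-adjusted effect is still wanted, write the intercept into the equation, define the effect as change, say whether Z is centred, and obtain the interval from a bootstrap that re-centres in each resample. Note that a cluster bootstrap is unreliable with few schools.

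The cost is a wording change in the SAP, one extra model, and adjusted intervals that are wider than the default output. No new data are needed.
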